 - Healthy patients free of any medical condition.

Exclusion criteria:

- Patients with medical conditions that may affect periodontal healing or regeneration.
- Patients with a history of allergic reactions, pregnant or breastfeeding females,
 smokers and alcoholics
- Patients with current or previous drugs intake that may predispose to gingival enlargement.
- Patients under orthodontic treatment or had orthodontic treatment in the past six months.
- Carious teeth, proximal restorations or fixed prosthesis.
- Patients with a history of traumatic oral hygiene measures or periodontal surgeries over the last six months at the area of interest or having any scar tissue.
- Poor oral hygiene patients.

11. Interventions

11a-General operative procedure

- The patients who fulfil the inclusion criteria will be enrolled.
- The nature of the study will be explained to each patient as well as the importance of compliance with pre- and post-operative instructions and follow-up visits.
- Each patient will be asked to sign an informed consent (appendix 1)
- After enrolment, periodontal examination and full periodontal charts will be recorded for each patient including Papilla Class I1, CP-BC plaque Index (*Leary et al., 1967*), gingival bleeding Index (*Ainamo & Bay, 1975*), probing depth (PD), clinical attachment level (CAL) and gingival recession.

Radiographic Evaluation

Standardized digital periapical radiographs will be obtained preoperatively and at follow-up using the long cone paralleling technique. All radiographs will be obtained using the same equipment, film exposure and development conditions.

Pre-surgical therapy

- All patient will receive strict oral hygiene instructions full mouth supra and sub-gingival debridement using hand instruments and ultrasonic scalers under local anesthesia.
- Four to six weeks following pre-surgical therapy, a periodontal re-evaluation will be performed to confirm the suitability of the chosen sites for this periodontal surgical study.
- The clinical and radiographic parameters will be recorded at baseline

The patients will be randomly assigned into two groups: A total of 36 sites (18 site per group)

Group A (Intervention): Patients will receive Tube technique.

Group B (Control): Patients will receive Hyaluronic acid.

Surgical Procedures

Group A (Intervention): Patients will receive Tube technique (Hooshang et al. 2020).

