- 1) Using a #15 blade, a semilunar incision is placed on the buccal aspect at the level of the mucogingival junction and a full-thickness flap was elevated. The flap is extended mesio-distally by an additional 4 to 5 mm than needed for the graft. This extension allowed the buccal flap to be freely moved into the recession area.
- 2) Another semilunar incision will be placed on the palatal aspect, such that the zenith of the

incision is located proximal to the alveolar crest.

- 3) An excavator (smaller than the width of the defect; evaluated pre-surgically on a study model) is used to carefully reflect the papilla away from the alveolar bone and root surfaces on the buccal aspect to access the interproximal region to prepare the bed for the graft. The excavator is used to do the same on the palatal aspect. The amount of reflection should yield a very relaxed papilla flap that permits placement of the papilla at the new coronal position without tension.
- 4) The recipient site at this time should resemble a "tube" with two openings; one on the buccal aspect at the mucogingival junction and one on the palatal aspect.
- 5) To harvest the graft, the incision is made parallel to and 2 mm away from the gingival margin. A thin flap containing the keratinized tissue is separated, then the second incision is made parallel to the gingival margin, but perpendicular to the alveolar bone. With a sharp periosteal elevator, the graft is raised with the periosteum and released at its anterior and posterior ends, and then from its base .The harvested graft should be larger than the side of interproximal defect in both cases: each graft will be 12 to 15 mm long, 5 mm wide, and 2 mm thick. A 4.0 chromic gut suture is used to pass the eye (swage) of the needle into the tube from the palate toward the buccal. The suture needle then engaged one end of the graft. An additional separate second suture is placed on the other end of the CT graft. One suture end (eye first) is passed through the tube toward the palatal side
- 6) The connective tissue graft is carefully slipped through the buccal aspect of the tube into the prepared interproximal bed towards the palate by means of the suture with the assistance of a periosteal elevator as needed. The thickest part of the graft is placed in the interproximal area.
- 7) The connective graft is sutured under the flaps onto the buccal and palatal tissues and the buccal and palatal flaps are sutured over the top of the graft.

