- Hyaluronic acid and saline are pre-loaded in insulin plastic syringes before injection for patient blinding. The needle is inserted 2-3 mm apical to the tip of the interdental papilla and directed coronally with an angulation of 45° to the long axis of the tooth, and the bevel directed apically. Then, the papilla is lightly moulded in an incisal direction for 1 minute using gauze.
- -In the follow-up phase, patients are recalled after 3,6months the first injection where clinical remeasurement of the black triangles and standardized digital clinical photographs will be retaken.

Postoperative care:

-Patient self-care instructions (Heitz et al. 2004):							
Avoid any hard brushing and trauma to the surgical site for two weeks.							
- Maintain a soft diet to avoid trauma to the surgical site.							
- After 24 hours patients can use warm saline rinses daily							
- Sutures will be removed fourteen days after the surgery.							
- Plaque control will be maintained by chlorohexidine mouth rinse after the surgery.							
12. Outcomes:							

Outcomes	Outcome name	Measuring device	Measuring units
1ry	interdental papilla loss	Photoshop CS5.	mm
outcome	(Decrease of black triangle		
	area) (mm2)		
2nd	Gain in papillary height	UNC Periodontal Probe	
outcomes			mm
	Change in the distance (CP-		
	BC)	Digital periapical radiograph	
		(linear measurement)	mm
	CAL		
		UNC Periodontal Probe	
	Pocket depth (PD)		mm
		UNC Periodontal probe	
	Gingival recession		mm
	(GR)	UNC Periodontal probe	
			mm
	Gingival bleeding		
		UNC Periodontal probe	G: : 1
			Gingival
	Plaque index		bleeding score
		UNC Periodontal probe	Diagna Inday
	Post-surgical patient		Plaque Index
	Satisfaction and post-	Post-surgical patient	score
	injection	satisfaction questionnaire	(1.7) noint 22-1-
		(PSPSQ) (Kiyak, Hohl, West,	(1-7) point scale
		& McNeill, 1984)	

-Digital clinical photographs: (SABT) mm (Abdelraouf et al. 2019)

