Clinical photographs will be obtained with the same digital camera (Nikon D5100 DSLR) mounted on a ring flashlight, using the same lens (Sigma Macro 105mm F2.8 EX) and the same focal length. The photographs are taken under the same lightning conditions and camera settings. The patients are sitting in an upright position, looking straight ahead. The Frankfort plane of the patient as well as the camera lens is positioned parallel to the ground. The photographs will be captured perpendicular to the teeth adjacent to the deficient papilla. Strict care is taken to ensure that the same up-down and right-left shooting positions are reproduced at different time intervals.

- -The surface area of the black triangle (SABT) is assessed using standardized digital clinical photographs analyzed by an image analysis program (Photoshop Cs 5, Adobe Systems, San Jose, CA, USA). The surface area of the black triangle was assessed from the photographs taken at baseline (before injection), 3 and 6 months from the first injection.
- 10 mm William's graduated periodontal probe was used as a scale for calibration.

Papilla Presence Index (PPI): (Cardaropoli etal. 2004)

- -PPI (1): is reported when papilla is completely present and coronally extends to the contact point to completely fill the inter-proximal embrasure which this papilla is at the same level as the adjacent papillae.
- -PPI (2): describes a papilla that is no longer completely present and lies apical to the contact point which this papilla is not at the same level as the adjacent papillae and the embrasure is no longer completely filled but the interproximal cemento-enamel junction is still not visible.
- -PPI (3): refers to the situation in which the papilla is moved more apical and the cemento-enamel junction becomes visible.
- -PPI (4): describes when the papilla lies apical to both the incisal cemento-enamel junction and buccal cemento-enamel junction which interproximal soft tissue recession is present together with buccal gingival recession and patients esthetics is dramatically compromised.

Clinical attachment level (CAL):

CAL will be determined by measuring the distance from the cemento-enamel junction to the base of the pocket using a UNC 15 periodontal probe.

Probing depth (PD):

Probing depth will be measured from the gingival margin to the base of the periodontal pocket using a UNC 15 periodontal probe.

Gingival recession (GR):

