Gingival recession will be measured using UNC periodontal probe from the cemento-enamel junction till the gingival margin (Miller, 1985).

Gingival Bleeding score:

- Gingival bleeding score will be performed through gentle probing of the orifice of the gingival crevice from all four surfaces of all teeth using UNC Periodontal probe.
- Recorded as (+) if bleeding is present or (-) if bleeding is absent.
- If bleeding occurs within 10 seconds a positive finding is recorded and the number of positive sites is recorded and then expressed as a percentage of the number of sites examined (*Ainamo & Bay, 1975*).

Patient Satisfaction:

- Three questionnaires will be asked to determine patients' satisfaction with the outcome of surgery
 - 1. Considering this was an elective operation, how likely would you be to recommend it to others?
 - 2. If you had to make the decision again, how likely would you be to undergo this surgery'?
 - 3. Considering everything, how satisfied are you with the outcome of your surgery
- These questions could all be answered by the patient using a 7-point response scale where: Very Satisfied = 7; Not At All Satisfied = 1. (*Kiyak et al., 1984*).

13. Participant timeline

13.	T0	T1	T2	T3	T4	T5	1-
Participant			(Surgical	Starting	3-	6-	
timelineTime			phase- 8	from T2	months	months	
point			weeks)	till 7th	post-	post-	
				day	surgical	surgical	
Enrollment	X						
Eligibility	X						
screen							
Informed	X						
consent							
Initial phase		X					
(Oral hygiene							
measures)							
standardized							
periapical							
radiograph							
study casts	X					X	
Allocation			X				
Intervention							
Injection			X				
Surgical tube							
technique							
Post-operative				X			
Care							
Papillary		X	X		X	X	
height, CAL,							
PD, GR							
measurements							

SABT					
Patient		X		X	
Satisfaction					

14. Sample size:

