This power analysis used interdental papilla loss after six months as the primary outcome. Based upon the results of Awartani FA and Tatakis DN (2016), the mean and standard deviation (SD) for control group were 0.71 (0.74) mm2. The minimal clinically significant difference was 1 mm2according to expert opinion. Using alpha (α) level of (5%), β level of 0.8 (Power = 80%); the effect size for independent samples t-test (d) was 1.32 and the minimum estimated sample size was 10 sites per group. Sample size was increased to 12 sites per group to compensate for a drop-out rate of 20% after six months. Sample size calculation was performed using PS Power and Sample Size Calculations Version 3.

15. Recruitment strategy

- The main investigator will be responsible for recruitment of patients.
- Patients will be selected from the outpatient clinic of the Oral Medicine and Periodontology
 Department, Faculty of Dentistry Cairo University.
- Screening of patients will continue until the target sample is achieved.
- Identifying and recruiting potential subjects will be achieved through patient database.
- 1. One year.
- 2. Candidate self-funding

B) Assignment of interventions

16. Allocation

16a. Randomization

The patients will be randomly allocated to either the intervention group or the control group using computer generated random numbers that will be performed by the supervisor. The patients will be allocated in a ratio of 1:1.

16b. Allocation concealment mechanism

The two groups will be equally prepared for both surgical procedures. Then the decision of which group will receive Hyaluronic acid injection and which will Tube Technique will be taken according to the randomized numbers placed in opaque sealed envelopes. The number will be picked by the supervisor.

16c. Implementation

The supervisor will be responsible for generation of allocation sequence as will as assign the patients to the 2 intervention groups. The main investigator will be responsible for patient enrollment.

17. Masking/blinding:

Due to the type of intervention only the outcome assessor and the statistician will be blinded. Single blinded:

- Blinding of the participants is not applicable.
- Blinding of the operator is not applicable.
- Outcome assessor (primary and secondary outcomes) and biostatistician will be blinded.

Key elements of Random Sequence Generation in protocol are:

- 1-Method of random sequence generation (computerized random number generator).

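### Section 17 claims a blinded assessor for every primary and secondary outcome, but patients rate one outcome unblinded, the recorder of clinical outcomes also oversees surgery, and no image masking is described

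*Protocol*

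**What the plan says.** Section 17 (Masking/blinding) states: "Outcome assessor (primary and secondary outcomes) and biostatistician will be blinded". It also states "Blinding of the participants is not applicable" and "Blinding of the operator is not applicable".

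Other parts of the protocol bear on this:

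- **Section 12 (Outcomes)** lists patient satisfaction among the secondary outcomes. Under Patient Satisfaction it says "These questions could all be answered by the patient using a 7-point response scale".
- **Section 5 (Roles and responsibilities)** assigns the co-supervisor two duties in one list: overseeing the surgery, and recording the clinical outcomes at baseline and follow-up.
- **Section 11, Group A, step 1:** "a semilunar incision is placed on the buccal aspect at the level of the mucogingival junction and a full-thickness flap was elevated". Steps 2 and 5 add a palatal incision and a graft donor site. Group B receives needle injections.
- **Section 10 (Exclusion criteria)** excludes patients with recent periodontal surgery "at the area of interest or having any scar tissue".
- **Section 12, digital clinical photographs:** "The photographs will be captured perpendicular to the teeth adjacent to the deficient papilla". Camera, lens, lighting and head position are standardised. Nothing is said about masking the images before they are measured in Photoshop.
- **Section 11, Group B:** "Hyaluronic acid and saline are pre-loaded in insulin plastic syringes before injection for patient blinding".

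**The concern.** Section 17 fixes a property, assessor blinding, for the whole set of primary and secondary outcomes. A report that follows it would describe satisfaction and the probed measurements as blinded, although the first is not blinded and the second may not be.

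The primary outcome matters most. SABT depends on where a reader places a soft-tissue border on an image, and the protocol's background expects more of the tube technique than of hyaluronic acid. If the reader knows the arm or the visit, expectation can enter the measurement. Photographs can be masked cheaply, yet the protocol describes no step that does so.

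**Working it through.** **Step 1. Compare the blinding claim with each outcome in section 12.**

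| Outcome | How it is obtained | Does the section 17 claim hold? |
|---|---|---|
| SABT (primary) | Photograph, outlined in Photoshop | Achievable; no masking of images described |
| CP-BC distance | Digital periapical radiograph | Achievable; soft-tissue incisions give no reason to give it up |
| Papillary height, CAL, PD, recession | Probe in the mouth | At risk; only one arm has incisions |
| Bleeding and plaque scores | Probe in the mouth | Same exposure as the row above |
| Patient satisfaction | Answered by the patient | False; section 17 says patients are not blinded |

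The last row is a contradiction on the face of the document and needs no assumption.

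**Step 2. Who assesses.** Section 5 has the co-supervisor oversee surgery and record outcomes. Someone who has overseen a patient's operation knows that patient's arm. The main supervisors also oversee surgery and the main investigator performs it, so no role listed in section 5 is free of treatment.

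**Step 3. What an assessor could see.** The tube arm has buccal, palatal and donor-site incisions and the control arm has none. Because patients with scar tissue are excluded, a mark seen at follow-up would point to the tube arm. Whether a mark can be seen at 3 or 6 months is not stated. Sutures are removed at day 14. The field of view of the photographs is not given, so it is unknown whether the mucogingival junction is in frame.

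**Step 4. Patient blinding.** Section 11 (Group B) prepares syringes so that patients are blinded, and mentions saline although no saline arm is defined. Section 17 says patients cannot be blinded. The two must be reconciled.

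**Step 5. Size (illustration only).** The blinding claim contains no figure. The inputs from sections 14 and 20 are a difference of 1 mm2, SD 0.74 mm2, alpha 0.05 and power 0.80. As a check on these inputs, a two-sided t-test needs 10.07 sites per group at the stated d = 1.32 and 9.66 at 1/0.74 = 1.35. The stated 10 therefore reproduces to within rounding.

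Assume, since the protocol gives no geometry, a gap 1.5 mm wide at the papilla and a border placed 0.1 mm more coronally in one arm:

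- 0.1 × 1.5 = 0.15 mm2
- 0.15/1 = 15% of the target difference
- 0.15/0.74 = 20% of the SD

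A 0.3 mm shift gives at most 0.3 × 1.5 = 0.45 mm2, and somewhat less because the triangle narrows.

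If a systematic shift b separates the arms and there is no true effect, the t-test has noncentrality (b/0.74)·√(n/2) on 2n − 2 degrees of freedom. It then rejects as follows:

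| b (mm2) | 10 per group | 18 per group |
|---|---|---|
| 0 | 5.0% | 5.0% |
| 0.1 | 5.9% | 6.8% |
| 0.2 | 8.8% | 12.4% |
| 0.3 | 13.8% | 21.9% |
| 0.5 | 29.9% | 50.4% |

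The second column uses the 18 sites per group given in section 11. A larger trial does not dilute such a bias.

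**The case against.** The strongest reply has four parts.

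- **Visibility is not shown.** No section says that incision lines persist at 3 or 6 months. The background credits this type of graft with good colour match and no keloid healing, and its remark on scarring concerns vertical releasing incisions in other techniques. A palatal incision would not appear in a facial photograph. This stands. A reader might infer that the incisions make the assessor blind impossible, or that the primary outcome is read unblinded. The documents support neither. They support a risk for probed outcomes and a missing safeguard for the photographs.
- **Coding exists.** Sections 27 and 29 put coded identifiers on forms and remove identifying data. This stands only in part: those provisions protect patient identity and do not say that arm or visit is hidden on an image.
- **Satisfaction is a matter of wording.** Section 17 itself says that patients are not blinded, so few readers would be misled. This reduces the harm but leaves the sentence wrong.
- **Recording may not mean measuring.** The co-supervisor might only write down what someone else measures. The protocol names no one else for the task, so the conflict remains until it is clarified.

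Cropping is also not a complete remedy. The bulk of the papilla stays visible in the cropped image, so some cue may remain.

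**Conclusion.** The blanket claim in section 17 should be narrowed. It is false for patient satisfaction, and it conflicts with the co-supervisor's duties in section 5. For the probed outcomes it is at risk, to a degree that the documents do not let one judge. For SABT and the radiographic CP-BC distance it can be met, but the protocol describes no image masking for SABT. The statistician's blind is not in question.

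The documents support no estimate of bias. The 0.15 mm2 figure and the rejection rates rest on an assumed width, an assumed shift and the assumption that the whole shift differs between arms. They show only that a small differential reading error would matter at this sample size, not that one will occur.

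**What to change.** **Section 12 (photographs and radiographs).** Calibrate each SABT photograph against the probe before cropping, or keep the scale in frame. Then crop to the embrasure and adjacent crowns and assign a random code. After the last 6-month visit, have a team member with no part in treatment measure all images in one shuffled batch without arm or visit labels. Someone other than that reader does the cropping and coding. Read the CP-BC radiographs under the same coding.

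**Section 17.** Limit the assessor-blind claim to SABT and the CP-BC distance, and keep the statistician's blind. State that outcomes probed at the chairside are at risk of unblinding and that patient satisfaction is open-label.

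**Sections 5 and 11.** Reconcile the co-supervisor's two duties with the assessor blind. One way that needs no extra person is to release the co-supervisor from overseeing surgery, which the main supervisors already cover. Reconcile the patient-blinding statement under Group B with section 17.

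**Cost.** A few minutes of handling per image, with no added visit or procedure. The report will claim blinding for fewer outcomes.

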It is a minimally invasive non-surgical injection of hyaluronic acid that observed to overcome the major limiting factor in most surgical techniques regarding the limited blood supply and the small working space. Supported by a recent study conducted by *Jinng etal.* 2019, who reported significant increase in the height of the gingival papilla and reduction of the area of the black triangle between baseline and 3 or 6 months in a group with thick gingival biotype after injection with hyaluronic acid, that was adding possible maximum effect with minimal postoperative hazards.

II.B. Objectives of the study:

7. Aim of the study

The aim of this randomized clinical trial is to compare the clinical effect of surgical Tube technique versus Hyaluronic Acid gel injection in reconstruction of the interproximal papilla in patients with class II papillary defect.

Picots:

P: Population: patients with class II papillary defect.

I: Intervention: Tube technique hosting sub-epithelial connective tissue graft.

C: Control: Hyaluronic acid injection.

Primary outcome: interdental papilla loss (Decrease of black triangle) (mm2)

Secondary outcome: assessment of gain in papillary height, radiographic distance between (CP-

BC), assessment of CAL. PD reduction, amount of gingival recession.

T: Time frame: 6 months.

S: Study design: Randomized clinical trial.

Hypothesis:

Null hypothesis: There is no difference in the gain in papillary height comparing hyaluronic acid injection versus Tube technique in patients with class II papillary defect.

8.Trial design

The study is designed as a superiority, 2 arm parallel groups, randomized clinical trial with allocation ratio 1:1.

III. Methods

A) Participants, interventions and outcomes

9. Study settings:

This study will be carried out on patients enrolled from the outpatient and postgraduate clinics of Oral Medicine and Periodontology department, Faculty of Dentistry, Cairo University.

10. Eligibility criteria:

Inclusion Criteria:

- Highly motivated patients with papillary deficiency types II, according to *Nordland* and *Tarnow 1998* classification will be selected, having at least one deficient papilla in the anterior region.
- Distance between the contact point and inter-proximal bone crest (CP-BC) of ≤ 7 mm and probing depth of ≤ 4 mm at the deficient papillary site (*Abdelraouf etal. 2019*).
 - Patients with full mouth plaque index (PI) and gingival index (GI) scores should be between 0-1.

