- 2- Allocation ratio (1:1, 2:1).
- 3- Type of randomization: simple, blocked, stratified.

c) Data collection, management, and analysis:

18. Data collection methods

- All the data of the patients included in the study will be recorded from them or extracted from the patient's periodontal chart.

- Telephone numbers of all patients included in the study will be recorded as a part of the written consent.
- All patients will receive a phone call at the time of the pre-determined follow up dates.

19. Data management:

Excel sheet program will be used though a computer system to manage the data with a secured password.

20. Statistical methods:

- The outcome used (State 1ry or 2ry): interdental papilla loss area (mm2)
- Values used for outcome (e.g. mean difference, percentage, proportion..... etc): mean and standard deviation
- Entry 1: (mean difference between 2 groups, mean and standard deviation of group 1, proportion 1 or estimated prevalence):

Minimal clinically significant difference = 1 mm2 according to expert opinion

• Entry 2: (standard deviation of control group, mean and standard deviation of group 2, proportion 2 or clinically important difference):

Mean of the control group = 0.71

SD of control group = 0.74

- Alpha level of significance: 0.05
- Effect size used in calculation: d = 1.32
- Power of the study: 0.8
- Statistical test used: Independent samples t-test
- The calculated sample size: 10 sites per group.
- Increased number for anticipated missing data: Sample size will be increased to 12 sites per group to compensate for a drop-out rate of 20% after six months.

D) Data monitoring:

21. Monitoring

No formal data monitoring committee will be needed since it is a study with known minimal risks.

22. Harms

Postoperative pain and/or swelling will be managed through analgesics.

23. Audit

Auditing of the study design will be done by the evidence-based committee – Faculty

Dentistry – Cairo University.

IV. Ethics and dissemination

24. Research ethics approval

This protocol and the template informed consent form will be reviewed by the Ethics Committee of Scientific Research -Faculty of Dentistry- Cairo University.

25. Protocol amendments

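### The primary variable is described both as a decrease in black triangle area and as papilla loss at six months, and the only test named has no baseline term; ANCOVA on baseline area would settle the analysis.

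*Protocol*

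**What the plan says.** The protocol describes the primary variable in four places.

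- Section 7 (PICOTS): "interdental papilla loss (Decrease of black triangle) (mm2", which is a change.
- Section 12 (outcome table): the same gloss, "Decrease of black triangle", applied to area.
- Section 14 (Sample size): "This power analysis used interdental papilla loss after six months as the primary outcome". On its face this is a level at one time point.
- Section 20 (Statistical methods): "The outcome used (State 1ry or 2ry): interdental papilla loss area (mm2", with neither a time point nor a change from baseline.

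Section 12 also shows that a baseline value will exist for every site: "The surface area of the black triangle was assessed from the photographs taken at baseline", and again at 3 and 6 months.

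The only test named anywhere is in section 20: "Statistical test used: Independent samples t-test". It stands in a list that otherwise holds sample-size inputs. Those inputs are repeated from section 14, where "the mean and standard deviation (SD) for control group were 0.71 (0.74) mm2" and "The minimal clinically significant difference was 1 mm2according to expert opinion". Nothing says whether the 0.71 is an area left at six months or an area gained since baseline.

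**The concern.** A level and a change are different variables, and a t-test gives a different estimate, standard error and p-value for each. The protocol does not say which one is tested. The gap between the two estimates is the baseline difference between arms, which can be sizeable in a trial this small. If the choice is made after the data are seen, there are two chances at significance.

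The same ambiguity reaches the sample size. The SD of 0.74 mm2 supports the stated number only for the variable it belongs to, and the 1 mm2 target is attainable only under one reading of 0.71.

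**Working it through.** **Inputs from the protocol.** Difference 1 mm2, control mean 0.71, SD 0.74, d = 1.32, alpha 0.05, power 0.80, 10 sites per group raised to 12 (sections 14 and 20). Section 11 gives 18 sites per group, so 12 and 18 are both shown.

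**Assumed, because the protocol does not give them.** Two-sided testing, normal data, independent sites, equal SDs at baseline and six months, and baseline to six-month correlation rho over a range.

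**1. The stated sample size.** The normal formula is n = 2(1.960 + 0.842)^2 / d^2. With d = 1.32, n = 9.01, so 10. With d = 1/0.74 = 1.351, n = 8.60, so 9. The exact t-test at 10 per group has power 0.797 (d = 1.32) or 0.815 (d = 1.351). The stated 10 reproduces.

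**2. How the estimates relate.** Decrease = baseline - six-month area. Taking tube minus control for each, the decrease estimate plus the area estimate equals the baseline difference between arms.

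**3. Size of that difference.** In SD units its standard error is sqrt(2/n): 0.408 at n = 12 and 0.333 at n = 18. The probability of an imbalance of at least 0.5 SD is P(|Z| >= 0.5/SE) = 0.22 and 0.13. With a baseline SD of 0.74, 0.5 SD is 0.37 mm2, or 37% of the 1 mm2 target.

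**4. How often the two t-tests disagree on p<0.05.** Simulation with 40,000 trials per cell, SD 0.74 at both times, rho 0.4 / 0.5 / 0.7:

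| True effect | 12 per arm | 18 per arm |
|---|---|---|
| 0 | 0.080 / 0.081 / 0.087 | 0.079 / 0.084 / 0.087 |
| 0.5 mm2 | 0.294 / 0.318 / 0.400 | 0.324 / 0.338 / 0.398 |
| 1 mm2 | 0.183 / 0.152 / 0.116 | 0.059 / 0.040 / 0.024 |

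With no effect, P(either significant) = (0.05 + 0.05 + 0.08)/2 = 0.09.

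**5. What 0.71 can mean.** As a remaining area, a 1 mm2 benefit needs a tube-arm mean of 0.71 - 1 = -0.29 mm2, which no area can take. As a decrease, it needs 0.71 + 1 = 1.71 mm2, which is possible.

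**6. What 0.74 can mean.** If it is the SD of area, the decrease has SD 0.74 x sqrt(2(1 - rho)). If it is the SD of decrease, the area has SD 0.74 / sqrt(2(1 - rho)). The ANCOVA residual SD is 0.74 x sqrt(1 - rho^2) in the first case and 0.74 x sqrt((1 + rho)/2) in the second. It is multiplied here by sqrt(1 + 1/(2n - 4)) = 1.031 at n = 10 for chance baseline imbalance, with 17 degrees of freedom. Power at 10 per group for 1 mm2, rho 0.3 / 0.5 / 0.7:

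| Meaning of 0.74 | t-test on the other variable | ANCOVA |
|---|---|---|
| SD of area | on decrease: 0.676 / 0.815 / 0.958 | 0.825 / 0.890 / 0.972 |
| SD of decrease | on area: 0.922 / 0.815 / 0.601 | 0.928 / 0.890 / 0.850 |

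Over rho 0 to 0.8, ANCOVA power is 0.789 or more under both readings. The minimum is at rho = 0 in the first row.

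**7. Precision of ANCOVA.** Ratio of standard errors, with SD equal at both times:

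| Against | Formula | n = 12, rho 0.4 / 0.5 / 0.6 / 0.7 | n = 18 |
|---|---|---|---|
| Six-month area | sqrt((1 - rho^2)(1 + 1/(2n - 4))) | 0.939 / 0.887 / 0.820 / 0.732 | 0.931 / 0.879 / 0.812 / 0.725 |
| Decrease | sqrt(((1 + rho)/2)(1 + 1/(2n - 4))) | 0.857 / 0.887 / 0.917 / 0.945 | 0.850 / 0.879 / 0.908 / 0.936 |

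Over that range the standard error falls by 6% to 27% against raw area and by 14% down to 6% against decrease at n = 12. At n = 18 the reductions are 7% to 27% and 15% down to 6%.

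**The case against.** The strongest reply is that the t-test line documents the power calculation and is not an analysis plan. Covariates are commonly fixed in a statistical analysis plan, which is not at hand. Under randomisation a t-test on either variable is valid, so the missing baseline term costs precision and causes no bias. That is right, and the missing covariate alone would be a modest remark. It does not remove the conflict over which variable is tested, because the protocol itself describes that variable in ways that do not agree.

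A second reply is that both places that define the outcome say decrease, and that section 14 may merely be giving its time point. The impossible -0.29 mm2 supports that reading. It is plausible, but nowhere stated, and section 20 again names an area.

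A third reply is that the disagreement rates rest on assumed SDs and correlations. They are largest at 0.5 mm2 and only 2% to 6% at the planned 1 mm2 with 18 per arm. The 9% error rate arises only if someone tries both tests and reports the better. A normal model with mean 0.71 and SD 0.74 also puts about 17% of areas below zero. These limits stand: the rates show the scale of the problem and do not forecast this trial.

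Finally, ANCOVA is not always more precise than a t-test on raw area. At 12 per arm it loses when rho is below sqrt(1/21) = 0.22. The loss is at most sqrt(1.05) - 1, about 2.5%.

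**Conclusion.** The concern holds. The protocol does not fix whether its primary variable is a six-month area or a decrease, and the one test it names gives different answers for the two. At 12 sites per arm a baseline imbalance that moves the estimates at least 0.37 mm2 apart has a probability of about 22% (13% at 18 per arm), if the baseline SD is 0.74. The probability in SD units rests on normality and independent sites only. The disagreement rates and the 9% error rate also need the assumed SDs and correlations.

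Either t-test would be unbiased. The faults are the open choice and a sample-size input whose meaning is unstated. This should be corrected before the data are unblinded, but it does not invalidate the design. That patients are randomised while sites are counted is a separate matter and is not settled here.

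**What to change.** - Define the primary variable once, in the same words in sections 7, 12, 14 and 20: black triangle surface area in mm2 at six months.
- Name the primary analysis as ANCOVA with arm and baseline area, reporting the adjusted mean difference with its 95% confidence interval. If the team prefers to enter the decrease as the response, the treatment effect is the same apart from sign, because baseline is in the model.
- State whether 0.71 (0.74) mm2 is a remaining area or a decrease; ANCOVA cannot answer this. If it is a remaining area, set a target difference below 0.71 mm2 with an SD for each arm and recompute the power. If it is a decrease, say that the target is 1.71 against 0.71 mm2.

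The cost is protocol wording and one degree of freedom, with no new data or visits. The sample size needs recalculation only if 0.71 proves to be a remaining area.
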